### 2.3.2. Unblinding

The study design was double-blind for the subject, the clinical site and the operational team. The Sponsor was planned to be unblinded to active treatment groups, following the analysis of Month 6 visit data from the main study (18-OBE2109-002 - Edelweiss 2 study), but was to be blinded to the treatment allocated to patients who had previously received placebo.

A database lock was to be performed prior to unblinding of treatment.

Following the early termination of the studies (main and extension), the lock was to be performed at the same time for the main and extension studies, and the unblinding done for all subjects for both studies.

### 2.4. Study Procedures

Sponsor:	ObsEva		
Protocol:	19-OBE2109-00	5	
Document Version No.:	1.0	Document Date:	18-MAY-2021

The schedule of assessments, as outlined in the study protocol, is provided in Table 1 and Table 2.

#### Table 1 Schedule of Assessments – Extension Treatment Period

Schedule of study assessments – Extension Treatment Period							
Timing 	Treatment Period						
i ining-		M7	M8	M9	M10	M11	M12
Informed Consent	х						
Inclusion-Exclusion criteria	x						
Physical examination (including weight)	х			х			х
Columbia-Suicide Severity Rating Scale	X	х	х	х	х	х	х
ECG 	X	х	х	х	х	х	х
Vital signs	х	х	х	х	х	х	х
Urine pregnancy test	x	х	х	х	х	х	х
Endometrium TVUS	X			х			х
Gynecological examination	x			x			x
Endometrial biopsy	x 						x 
Manual breast examination	x						х
Clinical laboratory & urinary protein dipstick	x 	х	х	x 	х	х	x 
BMD by DXA	X			x 			X
Adverse events	x	х	х	х	х	x	x
Concomitant medication	x	X	X	X	x	X	X

 All visits should take place at the end of the defined period (i.e. M7 visit should be scheduled at the end of Month 7, M8 visit should be scheduled at the end of Month 8, etc.). All visit dates should be calculated from the date of Day 1 visit (in the main study). A month is defined as 28 days/4 weeks. Visits should be scheduled ± 3 days (-3/+ 2 days for Month 7 visit) from the calculated date.

 All Month 6 assessments except informed consent and inclusion/exclusion criteria would have been performed as part of the main study (18-OBE2109-002 - Edelweiss 2).

 ECG should be performed at about the same time but before the PK sample

 If endometrium thickness in TVUS is  $\leq$  5 mm, no endometrial biopsy will be necessary.

 Overnight fasting is required.

 Only for subjects who met the following criterion at any site on the M6 DXA scan: -2.5 < Z-score ≤ -1.5

CRS-BS-TP-000005 V 1.0

## Page **17** of **66**

# Cytel

## Statistical Analysis Plan

Sponsor:	ObsEva		
Protocol:	19-OBE2109-00	5	
Document Version No.:	1.0	Document Date:	18-MAY-2021

Schedule of study assessments – Extension Treatment Period (cont'd)							
Timing 	Treatment Period						
1 iming 		M7	M8	M9	M10	M11	M12
Contraceptive dispensing and counselling	x	X	X	X	X	X	X
Permitted analgesic prescribing/dispensing	x	х	х	x	x	x	x
Vitamin D and calcium dispensing	X	х	х	х	х	х	х
Subject eDiary completion check	x	x	x	x	x	x	x
IMP accountability	x	X	Х	X	X	X	X
Dispense linzagolix/placebo kit	x	x	x	x	x	x	
Dispense ABT/placebo kit	x			X			
EHP-30, EQ-5D-5L and PROMIS 	x	X		x			x
mPGIS, PGIC, HRUQ and HRPQ 	X	Х	Х	X	X	X	X
SSIQ and PSIQ 	X						x
Blood sample for PK 	X	Х	Х	Х	Х	Х	Х
E2, LH, P4	x	x	x	x	x	x	x
SHBG	x			x			x
Bone biomarkers	X			X			X

 All visits should take place at the end of the defined period (i.e. M7 visit should be scheduled at the end of Month 7, M8 visit should be scheduled at the end of Month 8, etc.). All visit dates should be calculated from the date of Day 1 visit (in the main study). A month is defined as 28 days/4 weeks. Visits should be scheduled ± 3 days from the calculated date.

 All Month 6 assessments except informed consent and inclusion/exclusion criteria would have been performed as part of the main study.

 ClinROs (PSIQ and HRUQ) will be administered to the subject by the site staff and the responses will be filled in the eDiary. ePROs (EHP-30, EQ-5D-5L, PROMIS, PGIS, PGIC, HRPQ and SSIQ) will be filled in by the subject in the eDiary.

 PK samples should be taken after the ECG and before the daily dose of IMP.

CRS-BS-TP-000005 V 1.0

Sponsor:	ObsEva		
Protocol:	19-OBE2109-00	5	
Document Version No.:	1.0	Document Date:	18-MAY-2021

## Table 2 Schedule of study assessments - Extension Follow-up Period

Schedule of study assessments – Extension Follow-up Period						
Timing 	M1 ExFU	M3 ExFU	M6 ExFU			
Concomitant medication	X	x	X			
Adverse events	X	X	X			
Columbia-Suicide Severity Rating Scale	x	x	x			
ECG	x	X	X			
Physical examination (including weight)		x	X			
Vital signs	x	X	X			
Gynecological examination		X				
Manual breast examination		X				
Endometrium TVUS		X	X			
Endometrial biopsy	x 	x 	x 			
Clinical laboratory & urinary protein dipstick	x	x 				
Subject eDiary completion check	x	x	X			
Subject eDiary collection and deactivation			x			
EHP-30, EQ-5D-5L, PROMIS, HRUQ, HRPQ		x	x			
mPGIS and PPGIC	x	x	x			
BMD by DXA			x 			

 All follow-up study visits should take place at the end of the defined period (i.e. M1 ExFU visit should be scheduled at the end of the first month of follow-up, M3 ExFU visit should be scheduled at the end of the third month of follow-up, etc.). A month is defined as 28 days/4 weeks. Visits should be scheduled ± 7 days from the calculated date.

 Endometrium biopsy will be taken only if diagnosis at preceding visit was different than "benign endometrium" or if no endometrial biopsy was done at M12 nor at any visit since M12.

 An end-of-study biopsy is mandatory if no endometrium biopsy was obtained at M12 nor at any of the subsequent visits.

 Overnight fasting is required.

 Subjects with a BMD decrease from main study baseline of > 1.5% for lumbar spine and/or > 2.5% for total hip at M6 ExFU visit will have an additional DXA scan 6 months later.

CRS-BS-TP-000005 V 1.0

## Page **19** of **66**

# Cytel

## Statistical Analysis Plan

Sponsor:	ObsEva		
Protocol:	19-OBE2109-00	5	
Document Version No.:	1.0	Document Date:	18-MAY-2021

Schedule of study assessments – Extension Follow-up Period						
Timing 	M1 ExFU	M3 ExFU	M6 ExFU			
E2, LH, P4	x	x				
FSH at local laboratory for subjects that do not resume menses at M3 ExFU visit		X				
Bone biomarkers		x				
Permitted analgesic prescribing/dispensing	x	x				
Vitamin D and calcium dispensing	x	x				
Urine pregnancy test and contraceptive dispensing and counselling	x	x	x			

 All follow-up study visits should take place at the end of the defined period (i.e. M1 ExFU visit should be scheduled at the end of the first month of follow-up, M3 ExFU visit should be scheduled at the end of the third month of follow-up, etc.). A month is defined as 28 days/4 weeks. Visits should be scheduled ± 7 days from the calculated date.

CRS-BS-TP-000005 V 1.0

Sponsor:	ObsEva				
Protocol:	19-OBE2109-005				
Document Version No.:	1.0	Document Date:	18-MAY-2021		

#### 2.5. Efficacy, Pharmacokinetic, and Safety Variables

### 2.5.1. Efficacy Variables

The efficacy variables planned in the protocol, will not be analyzed due to the early study termination and the low number of subjects randomized.

### 2.5.2. Pharmacokinetic Variables

The pharmacokinetic variables planned in the protocol, will not be analyzed due to the early study termination and the low number of subjects randomized.

#### 2.5.3. Safety Variables

Safety endpoints include:

- Change from baseline to each scheduled assessment in BMD measured by DXA of lumbar spine (L1-L4), femoral neck, and total hip
- Incidence and severity of treatment emergent adverse events (TEAEs)
- Incidence and severity of hypoestrogenic TEAEs (hot flush)
- Changes in clinical laboratory assessments (hematology, biochemistry, coagulation parameters, hormones, lipids and urinalysis) from baseline to each scheduled assessment
- Any pathological changes from baseline in the endometrium as assessed by histology from endometrial biopsies
- Changes from baseline to each scheduled assessment in any other safety parameter including weight, vital signs, ECG, gynecological assessments and endometrial thickness

Safety analyses are described in Section 4.8.

Note that the endpoint "Time to the first post-treatment menses" was initially planned in the protocol, but will not be described in this SAP, because the study was stopped prematurely and all subjects couldn't be followed to evaluate this endpoint.

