12.1 ADVERSE EVENTS

12.1.1 Definitions

Adverse Event:

An adverse event (AE) is defined as any untoward medical occurrence in a clinical trial subject administered an investigational medicinal product (IMP) and which does not necessarily have a causal relationship with this treatment. It can therefore be any unfavourable sign (including an abnormal laboratory finding), symptom, or disease temporally associated with the use of an IMP, whether or not considered related to the IMP.

Any event occurring after signature of the informed consent form should be reported on an AE form or an SAE form, as appropriate.

Severity:

The severity of AEs must be assessed by the Investigator according to the following definitions. The term "severity" is used to describe the intensity of a specific event. This has to be distinguished from the term "serious".

Mild:	The subject is aware of the event or symptom, but the event or symptom is easily tolerated (e.g. no reduction in daily activities is required).
Moderate:	The subject experiences sufficient discomfort to interfere with or reduce her usual level of activity.
Severe:	Significant impairment of functioning: the subject is unable to carry out usual activities and/or the subject's life is at risk from the event.

Causality assessment:

The causality assessment of an AE to the linzagolix and/or ABT will be rated as follows by the Investigator:

Not related: There is no reasonable possibility of causal relationship between an AE and IMP.

Related: There is at least a reasonable possibility of a causal relationship between an AE and an IMP. This means that there are facts (evidence) or arguments to suggest a causal relationship.

Unexpected Adverse Event:

Any AE which is not consistent in specificity or severity with the current Investigator's Brochure (section 6.7.1), including all amendments, is considered unexpected.

Outcome:

Outcome describes the status of the AE. The Investigator will provide information regarding the subject outcome of each AE, and the options include:

Fatal	Termination of life as a result of an AE.
Not recovered/not resolved	Subject has not recuperated or the AE has not improved.
Recovering/resolving	Subject is recuperating or the AE is improving.
Recovered/resolved	Subject has recuperated or the AE has resolved.
Recovered with sequelae/resolved with sequelae	AE has resolved, but the subject has symptoms or pathology.
Unknown	Unknown, not observed, not recorded, or refused.

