### 4.8.2. Adverse Events

Adverse events will be coded using the Medical Dictionary for Regulatory Activities (MedDRA) and displayed in tables and listings using System/Organ/Class (SOC) and Preferred Term.

Analyses of adverse events will be performed for those events that are considered treatment emergent (TEAEs), where treatment emergent is defined as AEs with a start date on or after the first dose of extension study drug through 30 days after discontinuation of study drug or Month 12 visit date, or any event that was present at Month 6 but worsened in intensity or was subsequently considered drug-related by the investigator through the end of the extension study.

Adverse Event tables will be presented for the following periods: Month 6 to Month 12 (Extension treatment period) and Month 12 to Month 6 ExFU (Extension follow-up period) as defined in section 4.2.12.

Adverse events starting more than 30 days after end of treatment will be considered as post-treatment AE.

For each of these 2 study periods, an overall summary table will be prepared presenting, by treatment group, the number and percentage of subjects with

- any AE,
- any TEAE,
- any post-treatment AE (displayed only for the Extension follow-up period),
- Severe TEAE,
- any TEAE assessed by the Investigator as related to Linzagolix ((definite, probable, or possible relationship),
- any TEAE assessed by the Investigator as related to add-back therapy ((definite, probable, or possible relationship),
- any TEAE leading to permanent discontinuation of IMP,
- any serious adverse event (SAE),
- any serious treatment emergent adverse event (Serious TEAE),
- any serious treatment emergent adverse event (SAE) related to Linzagolix,
- any serious treatment emergent adverse event (SAE) related to add-back therapy,
- any fatal TEAE (where outcome is "Fatal")

CRS-BS-TP-000005 V 1.0

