#### Page **39** of **66**

Sponsor:	ObsEva		
Protocol:	19-OBE2109-00	5	
Document Version No.:	1.0	Document Date:	18-MAY-2021

In these tabulations, each subject will contribute only once (i.e., via the most related occurrence or the most intense occurrence) to each of the incidence rates in the descriptive analysis, regardless of the number of episodes experienced.

Adverse events are summarized by subject incidence rates, therefore, in any tabulation, a subject contributes only once to the count for a given adverse event (SOC or preferred term).

The number and percentage of subjects with any treatment-emergent adverse event will be summarized by treatment group and by SOC and PT.

If serious TEAEs are observed in the study, the number and percentage of subjects with any non-serious treatment-emergent adverse event will be summarized by treatment group.

Serious TEAE, TEAE assessed by the Investigator as related to treatment (definite, probable, or possible relationship), TEAE leading to permanent discontinuation of IMP, TEAE leading to permanent discontinuation of IMP leading to death and post-treatment AE will be only listed due to the low number of subjects included in the extension study.

The number of events will be also displayed for summaries on TEAE and for analysis of TEAE and nonserious TEAE by SOC and PT.

The ongoing status of each Adverse Event will be derived based on Adverse Event Outcome as the following:

AE Outcome	AE Ongoing Status
Fatal	Νο
Not recovered/not resolved	Yes
Recovering/resolving	Yes
Recovered/resolved	Νο
Recovered/resolved with sequelae	Νο
Unknown	Unknown
Missing	Missing

The ongoing status collected in eCRF will be ignored.

No formal hypothesis-testing analysis of adverse events incidence rates will be performed.

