### Section 14.3.1 Adverse Events

- Table 14.3.1.1.1 Summary of Treatment-Emergent Adverse Events from Month 6 to Month 12 Extension Safety Analysis Set
- Table 14.3.1.1.2 Summary of Treatment-Emergent Adverse Events from Month 12 to Month 6 ExFU - Follow-up Extension Safety Analysis Set
- Table 14.3.1.2.1 Treatment-Emergent Adverse Events by MedDRA SOC and Preferred Term from Month 6 to Month 12 Extension Safety Analysis Set
- Table 14.3.1.2.2 Treatment-Emergent Adverse Events by MedDRA SOC and Preferred Term from Month 12 to Month 6 ExFU Follow-up Extension Safety Analysis Set
- Table 14.3.1.3.1 Non-Serious Treatment-Emergent Adverse Events by MedDRA SOC and Preferred Term from Month 6 to Month 12 Extension Safety Analysis Set (if applicable)
- Table 14.3.1.3.2 Non-Serious Treatment-Emergent Adverse Events by MedDRA SOC and Preferred Term from Month 12 to Month 6 ExFU Follow-up Extension Safety Analysis Set (if applicable)

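### The SAP keeps severity of TEAEs and of hot flush as safety endpoints, but plans no severity summary beyond one pooled row per period and does not say so

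*SAP*

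**What the plan says.** SAP 2.5.3 lists two endpoints that pair incidence with severity: "Incidence and severity of treatment emergent adverse events (TEAEs") and "Incidence and severity of hypoestrogenic TEAEs (hot flush"). Protocol 7.2 has the same two. SAP 2.5.3 refers to Section 4.8 for the analyses.

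SAP 4.8.2 then plans three kinds of adverse event table:

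- **Overall summary.** "For each of these 2 study periods, an overall summary table will be prepared presenting, by treatment group, the number and percentage of subjects with" a set of event types. One of these is Severe TEAE, with no split by term.
- **TEAEs by term.** "The number and percentage of subjects with any treatment-emergent adverse event will be summarized by treatment group and by SOC and PT". Event counts are added. Severity is not mentioned.
- **Non-serious TEAEs by term**, if any serious TEAE occurs. Severity is again not mentioned.

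The overall summary has a counting rule: each woman contributes once, "via the most related occurrence or the most intense occurrence". Section 4.8.2 also names the categories that "will be only listed due to the low number of subjects included in the extension study": serious, related, leading to discontinuation or death, and post-treatment events.

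On data collection, Protocol 12.1.1 states that "The severity of AEs must be assessed by the Investigator according to the following definitions", with three levels (mild, moderate, severe). Protocol 12.2.3 makes severity part of every adverse event report.

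**The concern.** After early termination, SAP 1.2 narrows the plan to the safety and tolerability objectives, and those name hypoestrogenic adverse events specifically. A safety endpoint that the plan keeps should therefore have a stated result. Here the incidence half of each endpoint leads to a table. The severity half leads only to a count of women with any severe event of any kind.

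At stake is what the report can summarise. Following the table list exactly, it could give the number of women with hot flush in each group, but no table would show how many of those women had mild, moderate or severe hot flush. For TEAEs overall it could give the number with a severe event, but not how the remaining women divide between mild and moderate. Intensity also helps decide which events count, since under SAP 4.8.2 an event present at Month 6 becomes treatment-emergent if its intensity worsens. The grade is used to define the analysis and then barely reported.

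SAP 1.2 also undertakes to set out differences from the protocol's planned analyses, and this difference is not set out.

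**Working it through.** The plan gives no figure to reproduce, so the check traces each endpoint to its output.

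**Step 1: the adverse event tables in Appendix B, Section 14.3.1.**

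| Table | Content | Severity result | Hot-flush severity |
|---|---|---|---|
| 14.3.1.1.1 | Overall summary, Month 6 to Month 12 | Severe TEAE row, pooled (from 4.8.2) | none |
| 14.3.1.1.2 | Overall summary, Month 12 to Month 6 ExFU | Severe TEAE row, pooled (from 4.8.2) | none |
| 14.3.1.2.1 | TEAEs by term, treatment period | none | none |
| 14.3.1.2.2 | TEAEs by term, follow-up period | none | none |
| 14.3.1.3.1 | Non-serious TEAEs by term, treatment period, if applicable | none | none |
| 14.3.1.3.2 | Non-serious TEAEs by term, follow-up period, if applicable | none | none |

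Table 14.3.1.2.1 is titled "Treatment-Emergent Adverse Events by MedDRA SOC and Preferred Term from Month 6 to Month 12", with no severity dimension. Of six tables, none is by severity grade and none is specific to hot flush or hypoestrogenic events. Two carry one pooled severe row each.

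**Step 2: what each endpoint receives.**

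| Endpoint component | Output planned |
|---|---|
| TEAE incidence | Overall summary and tables by term |
| TEAE severity | One pooled severe row per period |
| Hot-flush incidence | Readable from the tables by term (women and events) |
| Hot-flush severity | No table; individual grades in listings |

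**Step 3: is the gap declared?** Section 5 removes the efficacy and pharmacokinetic analyses and, among safety endpoints, only time to first post-treatment menses. SAP 2.5.3 carries the same note about menses. The categories that 4.8.2 reduces to listings do not include severity or hot flush. Neither place covers the gap.

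**Step 4: size of the remedy.**

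- Replacing one severe row with three grades adds 3 − 1 = 2 rows per table.
- Hot flush by three grades adds 3 rows per table.
- Total: 2 + 3 = 5 rows in each of two tables, or 10 rows.
- The hot-flush rows need 3 grades × 4 treatment groups × 2 periods = 24 cells in all. A full split of the tables by term would need 24 cells for every preferred term.

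**The case against.** The best defence is that severity is reported, through listings. SAP 1.2 says all safety data will be listed, 4.2.1 says raw and derived data will be listed, and 4.2.7 says everything recorded in the CRF goes into listings. Listings 16.2.7.1 and 16.2.7.2 cover all adverse events and all TEAEs by subject. The SAP does not specify their columns, but these general statements make it reasonable to expect the grade to be shown. Section 4.8.2 also moves weightier categories to listings because few women were enrolled, so listing severity by term would fit that policy. This stands in part. A reader might infer that hot flush goes unreported or that its severity cannot be recovered, and the documents do not support either reading. What they lack is a summary, or a statement that severity is listed only.

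A reader might also use the protocol's Phase 2b hot-flush rates, 16.7% to 60.0% over 52 weeks (Protocol 5.5.3), to argue that the event will be common enough here to make the gap large. Those rates do not support that. Both ends come from regimens not given in this trial (50 mg, and 200 mg reduced to 100 mg). The matching fixed-dose 75 mg arm had 20.7%, also over the full 52 weeks. For the extension period, the same section reports that only 2 of 61 hot-flush events arose, among 176 women treated. Women who move from placebo to active drug at Month 6 could have new onset, but they are a subset of a study enrolled well below target.

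Nor does any passage say that hot flush is the event on which the two regimens are to be weighed against each other. The protocol calls it an expected, dose-dependent effect, and no formal testing is planned.

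Finally, splitting every term by grade in a small terminated study would give mostly empty cells. That objection is sound, and the fix below avoids such a split.

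**Conclusion.** The mismatch is real and narrow. Two retained safety endpoints include severity. The plan's only tabulated severity output is one pooled row per period, and hot-flush severity has no tabulated result. Neither Section 5 nor the list of categories reduced to listings declares this. Because Appendix B sets out the tables explicitly, this is more than detail left to programming.

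No efficacy conclusion or formal comparison depends on it, and the counts may be small. The case does not rest on hot flush being frequent. It rests on the plan naming an endpoint and not producing its summary. It assumes that Appendix B is the full set of adverse event tables, that hot flush is coded to a preferred term readable from the tables by term, and that the listings show the grade. If the listings did not show it, the gap would be wider.

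**What to change.** In Tables 14.3.1.1.1 and 14.3.1.1.2, replace the Severe TEAE row with women having any TEAE by maximum severity (mild, moderate, severe). Add rows for hot-flush TEAEs by maximum severity, by treatment group, in the same two tables. State which preferred term or terms count as hot flush. The counting rule already in 4.8.2, which takes the most intense occurrence, can serve unchanged. Amend 4.8.2 to describe these rows.

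A split of the tables by term into three grades is not needed at this enrolment. If severity by term stays in listings, say so in Sections 2.5.3 and 5, and state that the grade is a column in Listings 16.2.7.1 and 16.2.7.2.

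The cost is five extra rows in each of two tables and a sentence or two of text. The grades are already collected, so nothing new is asked of sites. The drawback is that some rows will hold very small counts, which should be shown as counts and read descriptively.

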7.2 SAFETY ENDPOINTS

- Change from baseline to each scheduled assessment in BMD measured by DXA of lumbar spine (L1-L4), femoral neck, and total hip
- Incidence and severity of treatment emergent adverse events (TEAEs)
- Incidence and severity of hypoestrogenic TEAEs (hot flush)
- Time to the first post-treatment menses
- Changes in clinical laboratory assessments (hematology, biochemistry, coagulation parameters, hormones, lipids and urinalysis) from baseline to each scheduled assessment
- Any pathological changes from baseline in the endometrium as assessed by histology from endometrial biopsies
- Changes from baseline to each scheduled assessment in any other safety parameter including weight, vital signs, ECG, gynecological assessments and endometrial thickness

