10.2.2 Post-treatment Follow-Up Period

Up to Month 6 Extension FU visit, the subject will continue to record on her eDiary, daily at approximately the same time each evening, her use of provided/prescribed analgesics, uterine bleeding, pelvic pain, dyspareunia, dyschezia and daily function.

The subject will be asked to bring her eDiary at each visit to the site during the entire Follow-Up Period.

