## **Table 4 Theoretical Visit Dates in Extension Follow-up Period**

Visit	Theoretical Date
Month 1 ExFU	Month 12 or treatment discontinuation date + 28
Month 3 ExFU	Month 12 date or treatment discontinuation date + 84
Month 6 ExFU	Month 12 date or treatment discontinuation date + 168

CRS-BS-TP-000005 V 1.0

Sponsor:	ObsEva		
Protocol:	19-OBE2109-005		
Document Version No.:	1.0	Document Date:	18-MAY-2021

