## 4.2.12. Last extension treatment administration date, End of extension Study date and Period definitions

The last extension treatment administration date will be defined as the date from the treatment termination reported in the extension period eCRF page. If this date is missing, the last date with a drug intake in the eDiary that is inferior or equal to Month 12 visit or the last available date with a drug intake in the eDiary if the subject discontinued the extension treatment will be used.

For subjects who entered the extension, the end of the extension study date will be the last assessment date in the extension study defined as last assessment recorded in the eCRF (excluding end date of adverse events and concomitant medications) or ediary date.

Note:

- For summaries by visit (efficacy or safety), the Month 6 assessments will be included in the main study analyses. For Adverse Events, Concomitant Medications and Daily diaries data collected on the Month 6 date will be part of the extension for subjects entering the extension study, and will be part of the main Follow-up period for subjects entering the main study follow-up period.
- For Adverse Events, Concomitant Medications and Daily diaries, data collected on the Month 12 date will be part of the Extension Follow-up period for subjects entering the Extension follow-up period.

The extension treatment period will be defined as Month 6 up to (Month 12 date -1) or treatment discontinuation date.

The extension follow-up period will be defined as the Month 12 date or (treatment discontinuation date+1) up to the extension follow-up end date (for subjects who entered the extension follow-up).

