## 5. CHANGES TO PLANNED ANALYSES

Following the early termination of the study and due to the number of subjects randomized being really less than the target number if the study had been fully enrolled, the analyses planned in the protocol on efficacy and pharmacokinetic assessments have been removed and only listings (if data available) for these assessments will be displayed. The statistical analysis plan (SAP) will be focused on the safety analysis.

For safety endpoints, the endpoint "Time to the first post-treatment menses" was initially planned in the protocol, but will not be described in this SAP, because the study was stopped prematurely and all subjects couldn't be followed to evaluate this endpoint.

Sponsor:	ObsEva				
Protocol:	19-OBE2109-005				
Document Version No.:	1.0 Document Date: 18-MAY-2021				

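### The planned safety endpoint on return of menses is dropped because follow-up was incomplete, which calls for censoring rather than removal

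*SAP*

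**What the plan says.** Protocol 7.2 lists "Time to the first post-treatment menses" among the safety endpoints. SAP 2.5.3 removes it "because the study was stopped prematurely" and not every woman could be followed for it, and SAP Section 5 repeats that reason and adds no other.

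The wording differs for the other deletions. SAP 2.5.1 says that the efficacy variables "will not be analyzed due to the early study termination and the low number of subjects randomized", and SAP 2.5.2 and 2.5.4 say the same of the pharmacokinetic and exploratory variables. Low numbers are not cited for the menses endpoint.

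The data needed are largely in place:

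- **Bleeding record.** Protocol 10.2.2: "Up to Month 6 Extension FU visit, the subject will continue to record on her eDiary", and uterine bleeding is among the daily items. Protocol 10.3.1.3 gives the scale: none, spotting, bleeding, heavy bleeding.
- **Time origin.** SAP 4.2.12: "The last extension treatment administration date will be defined as the date from the treatment termination reported in the extension period eCRF page", with a fallback to the eDiary.
- **Planned length.** SAP Table 4 places Month 6 ExFU at "Month 12 date or treatment discontinuation date + 168".
- **Analysis set.** The Follow-up Extension Safety Analysis Set (SAP 3.1) requires entry into follow-up, not its completion.

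**The concern.** Women who have not been followed to the event are the ordinary case in a time-to-event analysis. Each contributes time at risk until she is last observed. When the sponsor stops a study for everyone, the stopping date does not depend on whether a particular woman has resumed menses, so the censoring is plausibly non-informative. Incomplete follow-up is therefore a reason to analyse with censoring. It is not a reason to give up the endpoint.

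At stake is a planned safety result: the only summary of when menstruation returns after treatment. Protocol 10.2.2.2 itself treats Month 3 ExFU as a checkpoint, since absence of menses by then leads to an FSH test and advice to seek gynaecological evaluation.

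**Working it through.** **1. The plan's own figures.** No figure is given for this endpoint. The one size figure reproduces: 450 × 0.80 = 360 completers and 360 × 0.80 = 288 entrants (Protocol 13.2). From the visit days in Protocol 10.2, the follow-up visits fall at 365 − 337 = 28, 421 − 337 = 84 and 505 − 337 = 168 days after Month 12.

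**2. Is the reason applied consistently?** Under the same early stop the SAP keeps:

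| Post-treatment output | Where |
|---|---|
| Adverse events, Month 12 to Month 6 ExFU | Tables 14.3.1.1.2, 14.3.1.2.2 |
| Concomitant medications in follow-up | Table 14.4.13.2 |
| C-SSRS in follow-up | Table 14.4.15.2 |
| BMD to Month 6 ExFU, with 95% CIs | SAP 4.8.3, Table 14.4.1.1.1 |

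SAP 2.1 also says that the safety report will cover all subjects whatever their treatment duration. The reason used against the menses endpoint would apply equally to these outputs.

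**3. Does incomplete follow-up prevent valid estimation?** This is an illustration. None of its inputs is in the documents:

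- Time to menses T is exponential with median m = 28, 42 or 63 days, so λ = ln 2 / m.
- The administrative stop A is uniform on 0 to 252 days, capped at 168. The fully followed share is (252 − 168)/252 = 0.33.
- The number analysed, N, is 10, 20, 40 or 80, with 4,000 simulated trials for each combination of m and N.

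The true proportion by day 84 is F(84) = 1 − 2^(−84/m), which is 0.875, 0.750 and 0.603.

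A crude proportion that counts every unfollowed woman as event-free has expectation F(84) − (1/252) × (1/λ) × [1 − e^(−84λ)(1 + 84λ)]. For m = 42 this is 0.750 − (60.59 × [1 − 0.25 × 2.386])/252 = 0.750 − 0.097 = 0.653, in line with the simulated 0.652 to 0.657.

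| Median (days) | True F(84) | Kaplan-Meier mean, all N | Crude proportion | Women with observed event |
|---|---|---|---|---|
| 28 | 0.875 | 0.874–0.875 | 0.775–0.779 | 0.84 |
| 42 | 0.750 | 0.749–0.752 | 0.652–0.657 | 0.75–0.76 |
| 63 | 0.603 | 0.600–0.605 | 0.516–0.519 | 0.64 |

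Kaplan-Meier is within 0.003 of the truth throughout. The crude figure is low by about 0.08 to 0.10.

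**4. What small numbers cost.** The standard deviation of the day-84 estimate, and 1.96 times it as an approximate half-width:

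| N in the group analysed | SD | Half-width |
|---|---|---|
| 10 | 0.120–0.178 | 0.24–0.35 |
| 20 | 0.085–0.124 | 0.17–0.24 |
| 40 | 0.061–0.088 | 0.12–0.17 |
| 80 | 0.043–0.061 | 0.08–0.12 |

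Small groups widen the interval; they do not make the estimate invalid.

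**5. Is the event recorded?** The bleeding scale grades strength and does not label menses. In SAP Appendix A, the question on whether it is the menstrual period arises only for diaries left on the screening schedule. Where a diary ran on the main-study follow-up schedule, the menstrual-data action is marked not applicable, which suggests that the follow-up diary lacks that question. An event definition is therefore needed.

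**The case against.** The strongest opposing case has four parts.

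- **Low numbers are the SAP's general rationale.** SAP 1.2 ties its reduced scope to enrolment well below target, and SAP 4.8.2 reduces several adverse-event displays to listings for that reason. This stands as a possible ground for a cautious display. It is not the ground given for this endpoint, and SAP 4.8.3 keeps confidence intervals for BMD in the same small sample.
- **Recovery is still summarised.** A reader might infer that this was the only direct measure of ovarian recovery, or that only BMD now speaks to reversibility. The documents do not support that. Progesterone and LH at Months 1 and 3 ExFU (SAP 4.8.4, Table 14.4.6.1), endometrial thickness (SAP 4.8.8, Table 14.4.14.1) and biopsy diagnoses (SAP 4.8.9.1, Table 14.4.12.2) all extend into follow-up. They are snapshots at visits and do not give the timing of return.
- **The event is undefined in follow-up.** This stands. Two analysts could date the first menses differently, so restoring the endpoint takes more than adding one table.
- **The removal is disclosed, and listings are promised.** Also true. Section 5 declares the deletion, and SAP 1.2 promises all safety data in listings, so it cannot be said that all the information is discarded. However, Appendix B names no post-treatment bleeding listing: the menstrual cycle listing (16.2.4.2) sits among the baseline listings, and the daily diary listings (16.2.6.1, 16.2.6.2) do not name bleeding.

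The SAP's sentence could also mean that no woman was followed after treatment, in which case censoring would not help. That reading fits poorly with a SAP that defines a follow-up set, counts women entering follow-up and plans follow-up tables.

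**Conclusion.** The stated reason does not justify removing the endpoint. The certain loss is the derived endpoint and its summary, which is the only account of when menstruation returns. No hypothesis test depends on it (SAP 4.2.5), so this is a worthwhile and inexpensive repair to a descriptive safety report.

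The conclusion assumes that some women had post-treatment diary time and that the study-wide stop is unrelated to return of menses. Individual dropout for other reasons may not meet the second assumption and should be counted separately.

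Two further inferences should be avoided. First, a reader might infer that women followed for 28 to 84 days carry most of the information. The documents give no distribution of return times, no follow-up durations and no enrolled number, and the day-84 checkpoint does not supply them. Second, the endpoint does not describe recovery after 12 months of suppression in all women: two of the four groups took placebo in the main study and had at most 6 months of active drug.

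**What to change.** In SAP 2.5.3, Section 5 and Appendix B, restore the endpoint as a descriptive Kaplan-Meier summary in the Follow-up Extension Safety Analysis Set, by treatment group and overall.

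- **Origin:** last extension dose, as defined in SAP 4.2.12.
- **Event:** first post-treatment menses, defined in advance from the eDiary bleeding scale. Use the main-study definition if there is one; otherwise state a rule under which spotting alone does not count.
- **Censoring:** last eDiary entry, pregnancy or start of hormonal contraception, whichever comes first, with counts by reason. Protocol 10.6.2 bars hormonal contraception until 3 months after treatment, so estimates up to day 84 should be little affected by it.
- **Report:** numbers at risk, proportions at 28, 56 and 84 days with 95% CI, and the median only where estimable.
- **Listing:** last dose date, first menses date and last diary date for each woman.

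The cost is a written event rule, its derivation, one table or figure and one listing. No new data collection is needed. The downside is small groups and wide intervals, which the intervals and numbers at risk will show. If the numbers prove too small for any summary, the listing is the minimum, and the SAP should give that as the reason.
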